9.4 Safety and Tolerability Assessments

9.4.1 Adverse events

Where changes in severity are recorded in the Case Report Form (CRF), each separate severity of the AE will be reported in the listings, only the most severe will be used in the summary tables. A pre-existing condition is defined as an AE that starts before the subject has provided written informed consent and is ongoing at consent. A non-treatment emergent AE is defined as an AE which starts after informed consent but prior to dosing. A treatment-emergent AE is defined as an AE which occurs postdose or which is present prior to dosing and becomes more severe postdose.

All AEs will be listed. Treatment-emergent AEs will be summarized by treatment and severity. The frequency (the number of AEs, the number of subjects experiencing an AE and the percentage of subjects experiencing an AE) of treatment-emergent AEs will be summarized by treatment, Medical Dictionary for Regulatory Activities (MedDRA) version 21.0 system organ class and preferred term. The summary and frequency AE tables will be presented for all causalities. Any serious AEs will be listed.

9.4.2 Concomitant medication

Concomitant medication will be coded using the WHO drug dictionary (Version March 2018). Concomitant medication will be listed.

9.4.3 Clinical laboratory parameters

Clinical chemistry, hematology and urinalysis data outside the reference ranges will be listed.

9.4.4 Vital signs

Vital signs data will be summarized by treatment together with changes from baseline, where baseline is defined as the Day 1 predose assessment.

Vital signs data will be listed for individual subjects.

9.4.5 Electrocardiogram (ECG)

ECGs will be performed for safety monitoring purposes only and will not be presented. Any clinically significant findings from ECGs will be reported as an AE.

9.4.6 Hepatic Monitoring

If a subject experiences elevated alanine aminotransferase (ALT) $\geq 3 \times$ upper limit of normal (ULN), alkaline phosphatase (ALP) $\geq 2 \times$ ULN, or elevated total bilirubin (TBL) $\geq 2 \times$ ULN, liver tests will be performed to confirm the abnormality. Additional safety data may be collected if required, as defined in the protocol. Where applicable, the following will be presented.

The subjects' liver disease history and associated person liver disease history data will be listed. Any concomitant medication of acetaminophen/paracetamol will be listed. Results from any hepatic monitoring procedures, such as a magnetic resonance elastography (MRE) scan, and a biopsy assessment will be listed, if performed.

Hepatic risk factor assessment data will be listed. Liver related signs and symptoms data will be summarized by treatment and listed. Alcohol and recreational drug use data will also be listed.

All hepatic chemistry, hematology, coagulation, and serology data will be listed. Values outside the reference ranges will be flagged on the individual subject data listings.

9.4.7 Injection-Site Assessments

Injection sites will be assessed for induration, swelling, pruritus, and erythema/redness. Data will be summarized in a frequency table by treatment, and listed for individual subjects.

9.4.8 Injection-Site Pain

Visual analog scale (VAS) pain score will be summarized using standard descriptive statistics. In addition, the severity of pain will be categorized by VAS pain score as: mild pain (≤ 30), moderate pain (>30 and ≤ 70), and severe pain (>70). The number and percentage of the subjects in each pain severity category will be summarized by formulation and time point.

A mixed model for the repeating measures analysis model will be used to analyze the continuous injection-site pain VAS score. The model will include formulation and time post injection (0, 10, 20, 30, and 60 minutes) and formulation by time as fixed factors. The covariance

structure of the model will be unstructured. Other covariance matrices may be explored if needed. The Kenward-Roger method will be used to estimate the denominator degrees of freedom. Type III sums of squares for the least squares (LS) means will be used for the statistical comparison; the treatment differences along with their corresponding 95% CIs will also be reported.

[REDACTED]

9.4.9 Columbia-Suicide Severity Rating Scale (C-SSRS) / Self-Harm Supplement / Hospital Anxiety Depression Scale (HADS)

Given that few or no suicidal ideation or behaviours are anticipated, a listing of C-SSRS data will be produced by subject and visit. Only subjects that show suicidal ideation/behavior or self-injurious behavior without suicidal intent will be reviewed (i.e., if a subject's answers are all 'no' for the C-SSRS, then that subject will not be displayed). However, if a subject reported any suicidal ideation/ behavior or self-injurious behavior without suicidal intent at any time point then all their ideation and behavior will be reviewed, even if not positive.

HADS item scores will be listed for subjects with HADS depression subscale ≥ 11 at any time.

9.4.10 Evaluation of Immunogenicity

The frequency and percentage of subjects with preexisting ADA and with treatment emergent ADA+ to ixekizumab will be tabulated. Treatment-emergent ADAs are defined as those with a titer 2-fold greater than the minimum required dilution if no ADAs were detected at baseline (treatment-induced ADA) or those with a 4-fold increase in titer compared to baseline, if ADAs were detected at baseline (treatment-boosted ADA). For the TE ADA+ subjects the distribution of maximum titers will be described. The frequency of neutralizing antibodies will also be tabulated in TE ADA+ subjects.

The relationship between the presence of antibodies and the PK parameters of ixekizumab may be assessed.

9.4.11 Safety and Tolerability Statistical Methodology

Inferential statistical analyses is planned for the pain VAS score, using a mixed repeated measures model.

10. DATA REVIEW DURING THE STUDY

Review of the PK and safety data may be conducted during the conduct of this study to inform internal Chemistry, Manufacturing, and Control processes with respect to the new ixekizumab formulation development.

11. INTERIM ANALYSES

No interim statistical analyses are planned.

12. CHANGES FROM THE PROTOCOL SPECIFIED STATISTICAL ANALYSES

There were no changes from the protocol specified statistical analyses.

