9.2. Adverse Events

Investigators are responsible for monitoring the safety of subjects who have entered this study and for alerting Lilly or its designee to any event that seems unusual, even if this event may be considered an unanticipated benefit to the subject.

The investigator is responsible for the appropriate medical care of subjects during the study.

Investigators must document their review of each laboratory safety report.

The investigator remains responsible for following, through an appropriate health care option, AEs that are serious or otherwise medically important, considered related to the IP or the study, or that caused the subject to discontinue before completing the study. The subject should be followed until the event resolves, stabilizes with appropriate diagnostic evaluation, or is reasonably explained. The frequency of follow-up evaluations of the AE is left to the discretion of the investigator.

After the informed consent form (ICF) is signed, study site personnel will record, initially via source documents and then via eCRF, the occurrence and nature of each subject's preexisting conditions. Additionally, site personnel will record any change in the condition(s) and the occurrence and nature of any AEs.

The investigator will interpret and document whether or not an AE has a reasonable possibility of being related to study treatment or a study procedure, taking into account the disease, concomitant treatment or pathologies.

A "reasonable possibility" means that there is a potential cause and effect relationship between the IP and/or study procedure and the AE.

Planned surgeries should not be reported as AEs unless the underlying medical condition has worsened during the course of the study.

9.2.1. *Serious Adverse Events*

An SAE is any AE from this study that results in one of the following:

- death
- initial or prolonged inpatient hospitalization
- a life-threatening experience (that is, immediate risk of dying)
- persistent or significant disability/incapacity
- congenital anomaly/birth defect
- important medical events that may not be immediately life-threatening or result in death or hospitalization but may jeopardize the subject or may require intervention to prevent one of the other outcomes listed in the definition above.

Study site personnel must alert the Lilly CRP/CP, or its designee, of any SAE as soon as practically possible.

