Additionally, study site personnel must alert Lilly Global Patient Safety, or its designee, of any SAE within 24 hours of investigator awareness of the event via a sponsor-approved method. If alerts are issued via telephone, they are to be immediately followed with official notification on study-specific SAE forms. This 24-hour notification requirement refers to the initial SAE information and all follow-up SAE information.

Investigators are not obligated to actively seek AEs or SAEs in subjects once they have discontinued from and/or completed the study (the subject summary electronic case report form [eCRF] has been completed). However, if the investigator learns of any SAE, including a death, at any time after a subject has been discharged from the study, and he/she considers the event reasonably possibly related to the study treatment or study participation, the investigator must promptly notify Lilly.

Pregnancy (maternal or paternal exposure to IP) does not meet the definition of an AE. However, to fulfill regulatory requirements any pregnancy should be reported following the SAE process to collect data on the outcome for both mother and fetus.

9.2.1.1. **Adverse Events of Special Interest**

The following AEs of special interest will be used to determine the safety and tolerability of ixekizumab injections administered by PFS in this clinical study.

Adverse events of special interest for ixekizumab are:

- cytopenias (leukopenia, neutropenia, and thrombocytopenia)
- liver function test changes/enzyme elevations (alanine aminotransferase [ALT], aspartate aminotransferase [AST], total bilirubin level [TBL], and alkaline phosphatase [ALP])
- infection

- ISRs
- allergic reactions/hypersensitivities
- cerebrocardiovascular events
- malignancies
- depression
- inflammatory bowel disease (Crohn's disease and ulcerative colitis)
- interstitial lung disease

If infections, or allergic/hypersensitivity reactions are reported, these will be recorded as AEs. Investigators will also educate subjects about the symptoms of allergic/hypersensitivity reactions and will provide instructions on dealing with these reactions. A blood sample will be collected when possible for any subject who experiences an AE of allergic/hypersensitivity reaction during the study.

Injection-site reactions will be recorded as described in Section 9.4.5.1

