10.3.1. Safety Analyses

10.3.1.1. Clinical Evaluation of Safety

All IP and protocol procedure AEs will be listed, and if the frequency of events allows, safety data will be summarized using descriptive methodology.

The incidence of symptoms for each treatment will be presented by severity and by association with IP as perceived by the investigator. Symptoms reported to occur prior to study entry will be

distinguished from those reported as new or increased in severity during the study. Each symptom will be classified by the most suitable term from the medical regulatory dictionary.

The number of IP-related SAEs will be reported.

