10.3.1.2.2. Statistical Evaluation of Other Safety Parameters

Safety laboratory parameters and vital signs data will be listed and summarized using standard descriptive statistics, where possible. Injection-site assessments, including induration, swelling, pruritis, bleeding/bruising, and erythema/redness, will also be assessed. The parameters will be listed and summarized using descriptive statistics. Suicidal ideation and/or behavior and self-injurious behavior with no suicidal intent, based on the C-SSRS, will be listed by subject. Only subjects that show suicidal ideation/behavior or self-injurious behavior without suicidal intent will be included in the listing (ie, if a subject's answers are all 'no' for the C-SSRS, then that subject will not be displayed). HADS item scores will be listed for subjects with HADS depression subscale ≥ 11 at any time. Additional analysis may be performed if warranted upon review of the data.

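### SAP Section 12 declares no changes, yet the SAP text omits three descriptive safety summaries planned in the protocol: bleeding/bruising, laboratory values, and AE incidence by relatedness to IP

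*SAP*

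**What the plan says.** SAP Section 12 is a single unqualified sentence: "There were no changes from the protocol specified statistical analyses". Two other SAP sections give it weight. Section 3 makes the SAP take precedence over the protocol's statistical section and promises that substantial differences will be flagged. Section 9.1 lists everything in the database but restricts summaries to those the SAP describes.

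The protocol plans the following:

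- **Injection site (10.3.1.2.2).** After naming induration, swelling and pruritus, the text continues: "bleeding/bruising, and erythema/redness, will also be assessed. The parameters will be listed and summarized using descriptive statistics".
- **Laboratory (10.3.1.2.2).** "Safety laboratory parameters and vital signs data will be listed and summarized using standard descriptive statistics, where possible".
- **Adverse events (10.3.1.1).** The section opens with a condition, "if the frequency of events allows, safety data will be summarized using descriptive methodology", and then says: "The incidence of symptoms for each treatment will be presented by severity and by association with IP as perceived by the investigator". It ends: "The number of IP-related SAEs will be reported".

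**The concern.** The secondary objective is safety and tolerability of each test formulation against Reference, in a study prompted by injection-site pain. If the SAP is followed as written, three planned views of the data by formulation disappear while the SAP states that nothing changed.

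- **Bleeding/bruising** matters most. It is a local tolerability measure, and Protocol 7.3 blinds the staff who assess it. The SAP gives it no table by formulation.
- **Laboratory data** underlie some AEs of special interest, including cytopenias and liver enzyme changes. Protocol 9.2.1.1 says of these events: "The following AEs of special interest will be used to determine the safety and tolerability of ixekizumab injections". Those reported as AEs still reach the TEAE tables; the laboratory values themselves get no summary.
- **Relatedness** is recorded for every AE under Protocol 9.2: "The investigator will interpret and document whether or not an AE has a reasonable possibility of being related to study treatment". Amendment (b) followed an SAE in this study, which makes the planned count of IP-related SAEs worth stating.

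**Working it through.** No sample-size or error-rate calculation applies. The check is a comparison of texts, plus some counting.

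**1. Side by side**

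| Item | Protocol | SAP | Missing from the SAP |
|---|---|---|---|
| Bleeding/bruising | 10.3.1.2.2: one of 5 injection-site parameters to be listed and summarised | 9.4.7: frequency table by treatment for induration, swelling, pruritus, erythema/redness (4); bleeding and bruising appear nowhere in the supplied SAP text | 5 − 4 = 1 parameter |
| Laboratory | 10.3.1.2.2: listing and descriptive summary | 9.4.3: listing of out-of-range values | The summary |
| AEs | 10.3.1.1: incidence for each treatment by severity and by association with IP | 9.4.1: TEAEs by treatment and severity, and by treatment, system organ class and preferred term, for all causalities | The relatedness split only |
| IP-related SAEs | 10.3.1.1: number reported | 9.4.1: SAEs listed | The stated count |

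**2. Amount of data without a planned summary.** The schedule has bleeding/bruising assessed at 7 times on Day 1 (0, 10, 20, 30, 60, 120 and 240 minutes) and again on Days 3 and 8: 7 + 2 = 9 assessments. Appendix 5 gives 4 clinical laboratory samples. One is on Day −1, so 4 − 1 = 3 are postdose.

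**3. Does the laboratory qualifier explain the omission?** The same protocol sentence, with the same qualifier, covers vital signs. SAP 9.4.4 summarises these by treatment with change from baseline. The SAP does not say why numeric laboratory values could not be summarised as well.

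**4. Is it a version lag?** SAP Section 3 says it was written after review of the protocol and amendment (a). The amendment (b) summary in Protocol Appendix 6 lists no change to Section 10.3. Version lag does not explain the difference.

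**5. Is it redaction?** The visible redaction in this part of the SAP follows the pain model in 9.4.8. None is visible in 9.4.1, 9.4.3 or 9.4.7.

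**6. Separate point: Safety population.** Protocol 10.3 and SAP 8 both use all enrolled subjects. Protocol Appendix 1 defines enrolment as assignment to a treatment, and Protocol 10.1 and SAP 7 foresee randomised subjects who are not dosed. Such subjects enter the TEAE denominator but cannot have a postdose event. With a true rate r among 26 dosed subjects and k undosed, the reported rate is r × 26/(26 + k). The rates below are assumed, because the documents give none:

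| r | k = 1 | k = 2 |
|---|---|---|
| 20% | 19.3% | 18.6% |
| 30% | 28.9% | 27.9% |
| 50% | 48.1% | 46.4% |

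**The case against.** The strongest reply is that these are descriptive tables, that SAP Section 3 promises to flag only substantial differences, and that the protocol hedges its own plan.

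- **Bleeding/bruising.** Protocol 9.4.5.1 limits injection-site assessments to the four signs that SAP 9.4.7 uses; bleeding/bruising has its own section (9.4.5.2) and its own schedule row. The SAP apparently followed the narrower usage. That explains the omission but does not cure it, because the analysis section groups all five.
- **Laboratory.** SAP 9.4.6 lists hepatic chemistry and hematology where applicable, flags out-of-range values, and summarises liver-related signs and symptoms by treatment. This softens the gap but is not the general laboratory summary.
- **Relatedness.** The opening condition in Protocol 10.3.1.1 can be read as governing the whole section, although the relatedness sentence carries no condition of its own. It could justify dropping a sparse table once the data are seen; it does not explain planning none.
- **TFL shells.** These were not available and may hold the tables. SAP 9.1, however, looks to the SAP text, and Section 12 would still need reconciling.

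A reader might infer three stronger things that the documents do not support. The first is that AEs are not tabulated by formulation: they are, and only the relatedness split is absent. The second is that information is lost: the data are collected, SAP 9.1 lists all databased data, and related events can be counted from listings that show causality. The third is that a laboratory table would reveal modest shifts that a listing misses. The documents give no expected shift. With 26 per arm, the standard error of a difference in means is √(2/26) = 0.28 SD, so even an assumed shift of 0.5 SD is only about 1.8 standard errors. The case for the table is that the protocol planned it.

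**Conclusion.** The point holds as a mismatch between the SAP text, its own declaration and the protocol. Three planned summaries, plus the stated count of IP-related SAEs, have no counterpart in the SAP, and Section 12 says nothing changed. Bleeding/bruising is the clearest item.

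The consequence is limited to secondary safety and tolerability reporting. Neither laboratory values nor bleeding/bruising are named endpoints. The primary PK analysis, the all-causality TEAE tables, the other injection-site signs and the VAS model are unaffected. The conclusion rests on the SAP text as supplied; whether the tables would really be missing from the study report cannot be settled without the shells. It should be corrected, because the SAP supersedes the protocol and the correction is cheap.

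The Safety-population point is valid, but it is not a Section 12 error. The schedule places randomisation on Day 1, the dosing day, so few undosed subjects are expected and the dilution should be small.

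**What to change.** - **SAP 9.4.7:** add bleeding/bruising to the frequency table by treatment.
- **SAP 9.4.3:** add descriptive laboratory summaries by formulation. Change from baseline is optional, since the protocol does not plan it for laboratory data.
- **SAP 9.4.1:** add TEAEs by treatment and relatedness to IP, and state the number of IP-related SAEs.
- **SAP 12:** for any of these not restored, declare the omission and give the reason.
- **TFL shells:** check them against the corrected text.
- **Separate minor change, SAP 8 and Protocol 10.3:** define the Safety population as randomised subjects who received ixekizumab.

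The cost is a few sentences in the SAP, one in the protocol, and a few standard descriptive tables from data already being collected.

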14. DATA PRESENTATION

14.1 Derived Parameters

Individual derived parameters (e.g. PK parameters) and appropriate summary statistics will be reported to three significant figures. Observed concentration data, e.g. C_{\max} , should be reported as received. Observed time data, e.g. t_{\max} , should be reported as received. N and percentage values should be reported as whole numbers. Median values should be treated as an observed parameter and reported to the same number of decimal places as minimum and maximum values.

14.2 Missing Data

Missing data will not be displayed in listings.

14.3 Insufficient Data for Presentation

Some of the TFLs may not have sufficient numbers of subjects or data for presentation. If this occurs, the blank TFL shell will be presented with a message printed in the centre of the table, such as, "No serious adverse events occurred for this study."
